4.7 CRF testing and refining

The case report forms (including expenditure categories) were reviewed by a stakeholder group with representation from participating registries. The stakeholders were asked to contextualize the categories with examples relevant for their healthcare setting and to agree on operational definitions for spending as described above, including relevant source data documents. Expenditure will be recorded in local currency and then converted to USD using a single time point exchange rate (xe converter, xe.com).

4.8 Statistical analysis

Normally distributed continuous variables will be summarized using means and standard deviations while ordinal variables and skewed continuous data will be expressed as median with interquartile range. For categorical variables, percentages will be calculated and tests of significance between categorical variables will be done using a Fisher's exact or a Chi-square test as appropriate. Student's t-test will be used to compare normally distributed numerical variables between factors and a linear regression model will be fitted where applicable. Mann Whitney U-tests and Kruskal-Wallis tests will be used to compare numerical variables when normality cannot be assumed.

Analysis of the primary endpoint

a. Quantification of ICU OOPes

The primary endpoint will be summarized by reporting overall income group quintiles. Information on direct medical costs, including ICU bed charges, laboratory costs, medication

costs, procedure costs, consumables, medical nutrition, and other related costs will be obtained and summarized.

b. Calculation of CHE

The best method for CHE calculation for single patient episodes is debated in the literature. For the purpose of this study ICU episodes causing CHE will be defined as the calculated total episode OOPE divided by total *yearly* household income exceeding **10%**.²

Other applicable definitions that are justified in literature will also be considered and clearly documented in the Statistical Analysis Plan prior to statistical analysis.

c. CHE Sensitivity analysis

The primary analysis regarding CHE will be repeated using a variety of other considerations as a form of sensitivity analysis. These sensitivity analyses will be clearly outlined in the Statistical Analysis Plan prior to database lock and statistical analysis.

Analysis of risk factors for CHE

We will use mixed effects logistic regression models to investigate the relationship between risk factors and CHE. The multivariable mixed effects logistic regression model will then be used to simultaneously estimate the effects of multiple explanatory variables on CHE while controlling for the effects of other covariates. The mixed-effects models will help to account for clustering of the patient level, ICU level and country level data. Tests of significance will be performed at 5 % significance level. Where appropriate, the 95% confidence intervals will be calculated and reported. A detailed Statistical Analysis Plan will be developed for the primary and the secondary outcomes. The Statistical Analysis Plan will be finalized and signed by key investigators after database lock prior to statistical analyses.

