4.4 Study parameters/endpoints

Primary endpoints:

- Costs per complete patient episode, as actually spent in US dollars and International dollars (purchasing power parity exchange rate) in ventilated versus non-ventilated groups.
- Relative risk of CHE in ventilated versus non-ventilated groups.

Secondary endpoints:

- Risk factors for CHE (presumptive list in section 4.6)
- Frequency of different coping strategies for financial coverage of ICU costs

Tertiary endpoints

- Proportion of direct medical versus direct non-medical costs in the total OOPes
- Patient family socio-economic status (SES) or income
- Paying structures, models by country.

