4.6 Data to be collected

CRF structure and timeline is detailed in **Table 1** and comprises sequential domains from A to F. Daily follow up will run until ICU discharge or death, whichever occurs first. An additional telephone follow up at 30 days and 6 months will be used in survivors.

Table 1. CRF structure and timepoints for data collection

	ICU Admission day	Daily (max every 72h)	ICU Discharge	30 days	6 months	Responder
A Socioeconomic status and admission costs	X					Patient or caregiver
B Relative Wealth tool	X					
C Costs form	X	X				
D Discharge form			X			
E Follow up form				☎	☎	Patient or caregiver (telephone)
F Clinical registry Admission form (core) Daily processes of care Discharge (core)	X	X	X			Extracted from patient file

*In some instances daily followup may not be feasible due to unavailability of family members or unwillingness to discuss the study. Therefore a maximum interval of 72h is granted between two daily forms.

#A. Socioeconomic status and admission costs

Absolute household estimated yearly and monthly income will be collected in order to calculate CHE. Household consumption expenditure (food and non-food expenditure) will also be collected in order to minimize recall bias and potential missing income data. This information on expenditure will be used as a proxy of income, in cases where the income information is missing.

The following potential risk factors for CHE will be investigated: household income status, patient occupation; marital status; religion; access to safe water; educational status; ownership and location of households (urban vs. rural vs. slum); female-headed households; household size and age/gender of members; geographical location.¹⁰

#B. Relative wealth

Relative wealth will be quantified using the Equity tool (www.equitytool.org), consisting of a short survey of 11-12 questions allowing to compare the wealth of the respondents to the national or urban population in over 60 countries.

#C. Costs form

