10. APPENDIX

Appendix 1. Operational definitions

Term	Definition
OOPE	Defined as the cost incurred by individuals or households at the time of receiving any healthcare services in the ICU, including the component of cost-sharing (the part not covered by a third party like, an insurer) and informal payments (e.g., tips and under-the-table payments), but excluding insurance premiums and any reimbursements from the third-party payers (e.g., the government, a health insurance fund or a private insurance company). OOPE includes direct medical and direct non-medical costs, but excludes indirect costs (such as income/productivity loss).
Catastrophic health expenditure (CHE):	For CHE incidence estimation, there is no single agreed threshold. In this study CHE will be defined as OOPEs exceeding 10% of the household budget (yearly income or consumption expenditure). In sensitivity analysis, we will apply the higher threshold level of 25%.
Direct costs	Direct costs are expressed as expenditure during ICU treatment by households and consist of two main categories: direct medical cost and direct non-medical cost.
Direct medical costs	Subcategory of 'direct costs' referring to direct payments made by individuals to healthcare providers at the time of service use. These include those costs that are consumed for healthcare resources during ICU care and will be classified across 7 categories. 
 - Facility/provider fees, e.g. ICU bed charges, hospital daily rates, theater fees. - Laboratory costs - Medication costs e.g. drugs, fluids, nutrition solutions, bandages - Procedure costs e.g. diagnostic imaging procedures, mechanical ventilation, dialysis - Consumables e.g. (ventilator circuits, infusion sets, ventilation masks, gloves, alcohol rub, etc.) - Medical nutrition - Other costs These exclude any prepayment for health services, for example in the form of taxes or specific insurance premiums or contributions and where possible, net of any reimbursement to the individual who made the payments.
Direct non-medical costs	Subcategory of 'direct costs' including transportation, lodging, food items, informal payments and tips, payments incurred by caregivers and family for helping the patients during treatment.

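### The protocol has the SAP signed after database lock but promises part of its content before lock, and its CHE wording lets the stated primary definition be supplemented or reread in between

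*Protocol*

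**What the plan says.** **Timing.** Three statements in protocol Section 4.8 concern when the SAP fixes things.

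- Item c, on CHE sensitivity analyses: "These sensitivity analyses will be clearly outlined in the Statistical Analysis Plan prior to database lock and statistical analysis".
- Item b, on alternative CHE definitions: "Other applicable definitions that are justified in literature will also be considered and clearly documented in the Statistical Analysis Plan prior to statistical analysis". Database lock is not mentioned.
- The closing paragraph, on the SAP for primary and secondary outcomes: "The Statistical Analysis Plan will be finalized and signed by key investigators after database lock prior to statistical analyses".

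**Definition.** The second primary endpoint in Section 4.4 is "Relative risk of CHE in ventilated versus non-ventilated groups". Three places bear on what counts as CHE.

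- Section 4.8, item b: "For the purpose of this study ICU episodes causing CHE will be defined as the calculated total episode OOPE divided by total" yearly household income, with a cut-off of 10%.
- Appendix 1: "In this study CHE will be defined as OOPEs exceeding 10% of the household budget (yearly income or consumption expenditure". It then adds the sensitivity threshold: "In sensitivity analysis, we will apply the higher threshold level of 25" per cent.
- Section 4.6, part A, on consumption expenditure: "This information on expenditure will be used as a proxy of income, in cases where the income information is missing".

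**The concern.** CHE is a derived outcome. Each household's status depends on a threshold, a denominator and a rule for missing income. It is also one of the two primary endpoints and the basis of the sample size in Section 4.3.

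The study is an observational cohort. Ventilation status comes from the registry, costs are collected by research assistants, and no blinding of investigators to either is described. In that setting, the main safeguard against choices influenced by the data is an analysis plan that binds before the data are final and accessible. The closing paragraph of Section 4.8 places the binding step on the wrong side of lock, and item c of the same section assumes the opposite order.

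The timing matters more because the definition has two loose ends: alternative definitions with no assigned role, and a denominator worded differently in the operational definitions than in the analysis section. Either could be settled in a SAP signed after lock.

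**Working it through.** The protocol gives no figure on this point, so the check is mainly a comparison of its statements.

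**Step 1: order of events.**

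| Place in protocol | What the SAP fixes | By when |
|---|---|---|
| 4.8, item c | CHE sensitivity analyses | before lock and before analysis |
| 4.8, item b | other CHE definitions | before analysis; lock not mentioned |
| 4.8, closing paragraph | SAP for primary and secondary outcomes | after lock, before analysis |

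The first and third rows can both be true only if an unsigned draft fixes the sensitivity analyses before lock and the signed version follows after it. The protocol describes no such two-stage process, and an unsigned draft does not bind. The second row is compatible with the third, so on the current text alternative definitions can enter after lock.

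**Step 2: what is fixed and what is loose.**

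| Element | Status | Source |
|---|---|---|
| Threshold | 10% primary, 25% sensitivity | 4.8 item b; Appendix 1 |
| Cost scope | total OOPE, direct medical plus direct non-medical | 4.8 item b; Appendix 1 |
| Denominator | yearly household income | 4.8 item b |
| Denominator when income is missing | consumption expenditure | 4.6 part A |
| Denominator in the definitions table | either one, no condition attached | Appendix 1 |
| Role of other definitions | to be considered as well; not labelled | 4.8 item b |

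The first four rows form a complete definition. The last two are the loose ends. Sensitivity analyses have their own item (c), so a reader cannot tell whether definitions raised under item b are meant to stand beside the primary one.

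**Step 3: what the denominator wording can change.** For one household, let r = yearly expenditure / yearly income. Then

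OOPE / expenditure > 0.10 is equivalent to OOPE / income > 0.10 × r.

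The documents give no value for r. Taking 0.7 to 1.4 purely as an assumed range:

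- r = 0.7: 0.10 × 0.7 = 0.07, so the cut-off is effectively 7% of income.
- r = 1.0: 0.10 × 1.0 = 0.10, so nothing changes.
- r = 1.4: 0.10 × 1.4 = 0.14, so the cut-off is effectively 14% of income.

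A household whose OOPE lies between 10% of income and that shifted cut-off changes CHE status with the denominator. Under the Section 4.6 rule this affects only households with missing income. Under the Appendix 1 wording, taken alone, it could affect any household. How many would change cannot be derived from the documents.

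**The case against.** The strongest reply is that the protocol already states its primary definition. Item b of Section 4.8 gives numerator, denominator and threshold; Section 4.6 says when expenditure enters; and Appendix 1, read together with Section 4.6, means income with expenditure as fallback. The other definitions are additions, and nothing says they replace the stated one. The SAP must still be signed before analysis, and the hypotheses in Section 3.2 are labelled exploratory. Much of this stands, and it limits the point. It does not remove the timing conflict, give the other definitions a role, or put the missing-income condition into Appendix 1.

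Three stronger readings are tempting but not supported:

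- *That the CHE definition is left open until after lock.* It is not; it is stated in Section 4.8, item b.
- *That the analyst may choose freely among combinations of threshold, denominator and cost scope, with a correspondingly large false-positive rate.* Threshold and cost scope are closed: 25% is assigned to sensitivity analysis, and OOPE is defined as medical plus non-medical costs. An error rate that counts those combinations would count options the protocol rules out.
- *That the income fallback biases the comparison because caregivers answer for ventilated patients.* Section 4.2 has caregivers answer for any unconscious or unwell patient, and nothing shows that income is missing more often in either group.

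**Conclusion.** The timing contradiction is established from the text alone. The definitional part holds in a limited form: a stated primary definition can be supplemented or reinterpreted in a document signed when locked data, with cost and ventilation status unblinded, are accessible. That is weaker than a choice made after seeing formal results, which the protocol excludes by requiring signature before analysis.

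No numerical size can be given. It would need the share of missing incomes, the ratio of expenditure to income and the spread of OOPE relative to income, none of which the documents report. The point also assumes that no statement outside the protocol settles the order; the SAP itself is not at hand, and when it was actually signed is unknown. The correction is still worth making, because the protection is nearly free before lock and cannot be restored afterwards.

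**What to change.** 1. **Section 4.8, closing paragraph:** state that the SAP is finalised, signed and dated before database lock and before any tabulation of CHE or cost by ventilation status. This also brings it into line with item c.
2. **Section 4.8, item b, and Appendix 1:** name total episode OOPE over yearly household income, above 10%, as the sole primary CHE definition, with consumption expenditure used only where income is missing, as Section 4.6 already provides.
3. **Same two places:** label every other definition, including the 25% threshold, as a sensitivity analysis.

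This takes a few sentences. It needs no new data and no change to the case report forms or sample size. The only cost is that the SAP must be completed somewhat earlier.

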5. DATA MANAGEMENT

5.1 Data management

All patients will be identified with a unique study identification code. A logbook with the matching between patient number and name will be stored in the study site. The logbook will be the only document containing patient identifier information. Data will be stored an additional 10 years after the study's completion.

5.2 Data capture

Data will be collected from patients or caregivers interviews, or from the patient's medical chart and transcribed onto an Internet-based electronic CRF. Access to the data-entry system is protected by a personalized username and password. Patients are identified with a study identification code.

5.3 Data sharing

After publication of the primary results, on request a FAIR-compliant pooled dataset will be available for secondary analysis, after judgment and approval of scientific quality and validity of the proposed analysis by the CCAA Data Access Committee (email: [contact]).

6. PROJECT MANAGEMENT

6.1 Dissemination of results and publication policy

The results of this study will be published in a peer-reviewed medical journal. We have no restrictions in publication of outcomes of this study.

6.2 Timeline of project

Ethical Clearance: Sep 23 - Nov 23

Data Collection period: Dec 23 - Jun 24

Data analysis: Jun 24- Aug 24
 Preliminary results: Sep 24
 Final report: Dec 24

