1. STUDY SUMMARY

Title	ICU-related Out of Pocket Expenses (ICOPE) – a multinational prospective study in African and Asian countries		
Sponsor	Mahidol Oxford Tropical Research Unit Collaboration for Research, Implementation and Training in Critical Care in Asia and Africa (CCAA)		
Funder	Wellcome		
Trial design	Prospective observational study		
Trial Participants	All patients admitted to the participating ICUs during a predefined window of 14 days and expected to have a duration of stay >24 hours. Exclusion criteria is lack of informed consent.		
Sample size	at least 354 patients (at least 212 non-ventilated & 142 ventilated patients)		
Planned study period	Recruitment during 14 days Follow up until ICU discharge for each recruited patient, at 30 days after admission and 6 months after admission. Total study duration: 18 months		
Planned recruitment period	From 01 Dec 2023 to 30 June 2024		
	Objectives	Endpoints	Timepoint(s) of evaluation
Primary objective	To quantify ICU care related OOPE in African and Asian LMICs and the proportion of patients/families facing CHE, comparing patients receiving invasive ventilation to non-ventilated patients.	1.Costs per complete patient episode, as actually spent in US dollars and International dollars (purchasing power parity exchange rate) in ventilated versus non-ventilated groups. 2.Relative risk of CHE in ventilated versus non-ventilated groups.	During ICU stay, average 1 week
Secondary objectives	To identify risk factors for CHE.	Risk factors for CHE	Not applicable
	To identify coping strategies for OOPE and CHE	Frequency of different coping strategies for financial coverage of ICU costs	During ICU stay and follow up, 6 months

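### Section 6.2 closes data collection in June 2024 and analysis in August 2024, but the last 6-month call falls due about 30 December 2024

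*Protocol*

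**What the plan says.** The study summary (Protocol, section 1) sets recruitment as "From 01 Dec 2023 to 30 June 2024", with contacts "at 30 days after admission and 6 months after admission", and adds "Total study duration: 18 months" without saying when the 18 months begin. Section 4.6 restricts the 30-day and 6-month telephone contacts to survivors, and its Table 1 lists both among the timepoints for collecting data.

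Section 6.2 gives a different calendar: "Data Collection period: Dec 23 - Jun 24", then "Data analysis: Jun 24- Aug 24", "Preliminary results: Sep 24" and "Final report: Dec 24". It has no separate line for follow-up and none for a later 6-month analysis.

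Three further statements set the reach of the problem:
- The follow-up form (section 4.6, form E) is described as holding vital status and EQ5D-3L.
- The summary times the secondary coping-strategies endpoint at the ICU stay and follow-up to 6 months.
- Section 4.1 gives each site a recruitment window of 14 to 30 consecutive days. No site start dates are stated.

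**The concern.** Data collection in section 6.2 covers the same months as recruitment. Any patient admitted after December 2023 therefore reaches 6 months only after collection is said to have closed, and any patient admitted after February 2024 only after analysis is said to have ended.

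If a site team or data manager worked to section 6.2, the 6-month record would be cut off by calendar date. Each site recruits in one short block, so the loss would fall on whole sites that opened late rather than being spread across patients. If countries open at different times, which the protocol neither states nor excludes, it would also follow country. The 6-month results would then describe the early-starting sites only.

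**Working it through.** **Inputs.** Recruitment from 1 December 2023 to 30 June 2024 and contacts at 30 days and 6 months from admission (section 1); data collection to June 2024, analysis to August 2024, preliminary results in September 2024 and final report in December 2024 (section 6.2); planned size at least 354 (sections 1 and 4.3). The accrual pattern is not given. Uniform accrual is my assumption, with front-loaded and staggered patterns as the range.

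**Length of recruitment.** 31 + 31 + 29 + 31 + 30 + 31 + 30 = 213 days.

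**Due dates.** Due date = admission date + 6 calendar months.
- First 6-month call: 1 December 2023 + 6 months = 1 June 2024.
- Last 6-month call: 30 June 2024 + 6 months = 30 December 2024. That is six months after collection closes and four months after analysis closes.
- Last 30-day call: 30 June 2024 + 30 days = 30 July 2024, one month after collection closes.

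This part needs no assumption beyond the protocol's own dates.

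**Share of patients due by each date.** Share = recruitment days whose due date falls on or before the cut-off ÷ all recruitment days. The protocol gives no such share to reproduce.

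Uniform accrual, 6-month call:
- By 30 June 2024 (admitted by 31 December 2023): 31/213 = 14.6%, about 52 of 354.
- By 31 August 2024 (admitted by 29 February 2024): 91/213 = 42.7%, about 151 of 354.
- By 30 September 2024 (admitted by 31 March 2024): 122/213 = 57.3%.
- By 30 November 2024 (admitted by 31 May 2024): 183/213 = 85.9%.

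Counting 6 months as 183 days changes the first two to 14.1% and 43.2%. For the 30-day call, 183/213 = 85.9% are due by 30 June 2024; June admissions are not.

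Other accrual patterns:

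| Accrual assumed | Due by 30 June 2024 | Due by 31 August 2024 |
|---|---|---|
| Uniform to 30 June 2024 | 31/213 = 15% | 91/213 = 43% |
| 14-day site windows, starts spread evenly | 12% | 42% |
| 30-day site windows, starts spread evenly | 9% | 42% |
| Uniform, ended by 31 January 2024 | 31/62 = 50% | 62/62 = 100% |
| Uniform, ended by 31 March 2024 | 31/122 = 25% | 91/122 = 75% |
| Uniform, ended by 30 April 2024 | 31/152 = 20% | 91/152 = 60% |

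All shares are upper limits on completed 6-month calls, because only survivors are telephoned.

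**By site.** A site that opens after 31 December 2023 has no 6-month call due by 30 June 2024. A site that opens after 29 February 2024 has none due by 31 August 2024.

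**Total duration.** Section 6.2 spans September 2023 to December 2024, which is 16 months, or 13 months from the first month of recruitment. Eighteen months runs to about February 2025 if counted from September 2023, and to about May 2025 if counted from December 2023. Either end lies after the last 6-month call.

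**The case against.** The best defence is that section 6.2 uses data collection to mean the in-ICU window, since its months match the recruitment period. Nothing in the protocol says that calls stop on a date, sections 1 and 4.6 require them, and database lock (section 4.8) is undated. This stands in part: truncation is what would follow from working to section 6.2, not something the protocol orders. It does not remove the conflict. Table 1 counts the telephone contacts as data collection, section 6.2 lists no later analysis, and a final report in December 2024 would coincide with the last calls.

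A reader might infer several stronger things that the documents do not support:
- **That only a minority of patients could have 6-month data.** This depends on accrual. At the August date it fails if more than half of patients were admitted by 29 February 2024; the front-loaded patterns above give 60% to 100%. Even under uniform accrual, 57% are due by the end of September and 86% by the end of November 2024.
- **That the main results are at risk.** The primary OOPE and CHE endpoints are timed to the ICU stay. Vital status and EQ5D-3L at 6 months are not among the endpoints in section 4.4.
- **That the coping endpoint would certainly be lost.** It is also collected during the ICU stay, and form E as described has no coping item. The exposure rests only on the 6-month timepoint in the summary, and a longer timeline would not by itself supply those data.
- **That 18 months flatly contradicts section 6.2.** The start of the 18 months is undefined, and 16 months of listed activity fits inside it. It is a mismatch to explain.

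**Conclusion.** The dates are wrong as written. With recruitment to 30 June 2024 and a contact 6 months after admission, follow-up cannot finish inside the data collection or analysis periods in section 6.2, and the final 30-day calls also overrun collection.

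The number of patients affected is conditional. Under uniform accrual about 15% have reached 6 months when collection closes and about 43% when analysis closes; across the patterns examined the ranges are 9% to 50% and 42% to 100%. If section 6.2 were followed, 6-month vital status and EQ5D-3L, and coping data so far as they use the 6-month timepoint, would be missing by site start date. This is a timetable inconsistency affecting secondary and descriptive follow-up data. It should be corrected, and it is no threat to the primary analysis.

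**What to change.** In section 6.2, extend data collection to the last 6-month call, about 31 December 2024. Schedule the 6-month database lock, analysis and final report after that date, and label the 2024 analysis as covering the ICU-stay endpoints. State in section 1 when the 18 months begin; the later report must fit by about February 2025 if they start in September 2023, or about May 2025 if they start in December 2023.

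If the 2024 dates must stand, remove the 6-month contact consistently from section 1, the text of section 4.6 and Table 1. Deleting it from the secondary endpoint alone would leave the calls in place and the conflict unresolved. The June close would still need to allow for 30-day calls running to about 30 July 2024.

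The cost is a change of timeline wording and a 6-month report that arrives a few months later.
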